5.2 Exclusion Criteria

Participants meeting any of the exclusion criteria listed below at screening will be excluded from study participation.

PARTICIPANT MRN		PARTICIPANT INITIALS
No	Criteria	
	5.2.1	Simultaneously enrolled in any therapeutic clinical trial
	5.2.2	Diagnosed with a psychiatric illness or is in a social situation that would limit compliance with study requirements
	5.2.3	Is pregnant or breastfeeding
	5.2.4	Prior history of lung/chest wall surgery
	5.2.5	Prior history of radiation treatment to the chest
	5.2.6	History of autoimmune disease
	5.2.7	Current use of immunosuppressive drugs
	5.2.8	Prior history of immunotherapy
	5.2.9	Prior history of metastatic cancer or concurrent active secondary malignancy

Eligibility Confirmed	Print Name	Signature	Date
Clinical Research Coordinator			
Double Check			
Treating Physician			

Once eligibility has been confirmed, use the link below to register your participant.
 Please allow up to 24 business hours for the registration process.

6 CHILD-BEARING POTENTIAL / PREGNANCY

Because the effect of the study intervention is considered possibly teratogenic and has potential risks to the fetus, pregnant females will not be included in the study. However, no female of childbearing potential will be excluded from the study.

An effective form of contraception of the woman's choice will be required during study participation. Participants should not get pregnant, breastfeed, donate sperm or father a child while participating in this study and for **6 months** after the last dose of the study medication.

Women of childbearing potential and male participants must agree to use adequate contraception (hormonal or barrier method of birth control; abstinence) prior to study entry and for the duration of study participation. If a woman becomes pregnant or suspects she is pregnant while participating in this study or if her male partner is a participant in this study, the treating physician should be informed immediately.

Child-bearing potential is defined as any female (regardless of sexual orientation, having undergone a tubal ligation, or remaining celibate by choice) who meets the following criteria:

- Has either not undergone a hysterectomy or bilateral oophorectomy or has not been naturally postmenopausal for at least 12 consecutive months.

Participants must agree to use one of the following acceptable forms of birth control.

- Sexual Abstinence
- One barrier method (cervical cap with spermicide plus male condom; diaphragm with spermicide plus male condom) PLUS hormonal method (oral contraceptives, implants, or injections) or an intrauterine device (e.g., Copper-T).

If a woman becomes pregnant or suspects she is pregnant while participating in this study, she should inform her treating physician immediately.

If the partner of a man becomes pregnant or suspects she is pregnant while he is participating in this study, he should inform his treating physician immediately.

Men of child-bearing potential must not father a child or donate sperm while receiving investigational product and for **6 months** after their last study intervention.

6.1 Screen Failures

Patients who screen fail cannot be re-screened at a later date.

Screen failures will be offered standard of care treatment per institutional guidelines and physician discretion. They will not be counted towards enrollment and will not be included in analysis of the data.

6.2 Participant Replacement

Participants will not be replaced once they have successfully completed surgery.

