15	DATA HANDLING AND RECORD KEEPING.....	35
15.1	Data Collection and Management Responsibilities	35
15.2	Protocol Deviations.....	36
15.3	Study Closure	36
15.4	Study Records Retention.....	36
16	APPENDICES	37
	Appendix A: ECOG Performance Status.....	37
	Appendix B: Reportable Events	38
	Adverse Event (AE) Definition	38
	Serious Adverse Event (SAE) Definition	38
	Unanticipated Problem 39	
	Suspected Adverse Reaction.....	39
	Expectedness and Attribution	39
	Expectedness 39	
	Attribution 40	
	Adverse Event Monitoring 40	
	Appendix C: Clavien-Dindo Classification for Surgical Complications.....	42
	Appendix D: Examples of Grading Using Clavien-Dindo Classification	43
	Appendix E: Wound Healing Assessment - GTSD Training Manual- Pages 246-248	44
17	LITERATURE REFERENCES.....	47

SCHEMATIC OF STUDY DESIGN

**Pre-Operative Immuno-Modulatory SBRT
(POIMS Trial)
A pilot trial in early stage NSCLC**

PROTOCOL SUMMARY

Title	Pre-Operative Immuno-Modulatory SBRT (POIMS Trial): A pilot trial in early stage NSCLC
Protocol Number	IIT-2020-POIMS-Lung
Phase	Pilot
Design	Single arm pilot trial
Study Duration	
Approximately 5 years
 
 • Enrollment Period – approximately 18 months • Follow up period for adverse events to 36 months after surgery • Follow up period for post-operative surgical complication / wound healing events- 3-6 months after surgery • Follow-up period for disease outcome–36 months after surgery
Study Center	University of Kansas Cancer Center
Objectives	
Primary: Assess the impact of non-ablative SBRT (800 cGy X 3 fractions) on immunomodulation in NSCLC tumor cells
 
Secondary: Assess the impact of non-ablative SBRT (800 cGy X 3 fractions) prior to surgical resection on peri- and post-operative surgical complication rate, wound healing, and disease outcomes.

Number of Participants	10

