2 HYPOTHESIS

Primary: Non-ablative SBRT (800 cGy X 3 fractions) given 5-7 days preoperatively in selected patients with stage I-II NSCLC will result in alterations in the tumor immunoprofile, tumor microenvironment, gene expression profiles and peripheral blood immune repertoire.

Secondary: This regimen will be well tolerated, associated with minimal toxicity, and will not impact on wound healing.

It should be noted that this is designed as a pilot trial, so statistical analysis will be descriptive and formal hypothesis-testing will not be performed

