3.2 Secondary Objectives

- Assess the impact of non-ablative SBRT (800 cGy X 3 fractions) prior to surgical resection on peri- and post-operative complication rate, and wound healing.
 - Surgical complications will be assessed using the Clavien-Dindo Classification system. The Clavien-Dindo classification system has been validated and established as an “objective, reproducible” grading classification.¹⁷
 - This classification system uses a grading based on the extent of intervention needed to manage a specific complication. See appendices C and D for examples.
 - Wound healing will be assessed and charted by the study cardio-vascular (CV) surgeons using the General Thoracic Surgery Database with particular references to pages 246-248. See Appendix E.
- Describe loco-regional control, metastasis-free survival, disease-free and overall survival in patients treated on this trial with pre-operative SBRT followed by surgery

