3.4 Secondary Endpoints

What is being measured	Measurement time frame	Measurement Tool

The impact of pre-surgical non-ablative SBRT on peri- and post-operative surgical complication rate
	
From Day of post-SBRT surgery through 6 month (± 2 months) post-operative follow up visit
	
Medical Record Review Clavien-Dindo Classification system

The impact of pre-surgical non-ablative SBRT on wound healing
	
From Day of post-SBRT surgery through 6 month (± 2 months) post-operative follow up visit
	
Medical record review General Thoracic Surgery Database.

Loco-regional control, metastasis-free survival, disease free and overall survival
	
From Day of enrollment through 36 month follow up visit
	
Medical record review

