- Surgery will occur 5 to 7 days post completion of the last fractionation of radiation treatment. Surgery will consist of a lobectomy or sub lobar resection. The technique will be at the discretion of the study cardiothoracic surgeon, and may employ either an open approach, video assisted thoracoscopic or robotic-assisted approach. Surgical sampling of the at risk hilar and mediastinal nodes may be performed at the time of resection but is not a requirement of the study.
- In the event adjuvant systemic therapy is elected, follow up studies as defined in this protocol may be modified as clinical necessity requires. Participants will be continued for secondary objectives and will be reported using descriptive statistical analysis.

Pathology Processing

- After resection, the tumor will be oriented by the surgeon and submitted to the pathology lab. In the pathology lab it will undergo gross examination in a standard manner. The specimen will be submitted for microscopic examination. Samples for translational research use will be processed and transferred to the appropriate laboratory as defined in the study laboratory manual.

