Pre-operative anesthesia clinic clearance for surgery is required and *may* include

- EKG
- Stress Test
- Cardiac Clearance

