12.2 Study Stopping Rules

If a participant experiences one or more of the following events, possibly related to study intervention, study will be suspended pending data safety monitoring committee (DSMC) review to determine if study should continue:

- a. Wound healing delay beyond standard timeframe as deemed by study Cardio-Vascular (CV) surgeons
- b. Peri operative/post-operative surgical complications beyond acceptable institutional rates as determined by study CV surgeons
- c. Death from study intervention

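### Section 6.2 permits replacement of irradiated participants until surgery is 'successfully' completed, and section 3.2 can be read to leave those never resected out of the survival description

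*Protocol*

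**What the plan says.** - **Replacement.** Protocol section 6.2 is one sentence: "Participants will not be replaced once they have successfully completed surgery". It gives no definition of success, no list of permitted reasons, no cap, and no analysis status for the person replaced.
- **Size.** The Protocol Summary row "Number of Participants" gives 10.
- **Sequence.** Radiation comes first. Section 8.1 then states: "Surgery will occur 5 to 7 days post completion of the last fractionation of radiation treatment". Section 9.1 adds: "Pre-operative anesthesia clinic clearance for surgery is required", which may be obtained at any time between enrollment and surgery, and so after SBRT.
- **Disease control and survival.** The objective in section 3.2 covers loco-regional control, metastasis-free survival, and "disease-free and overall survival in patients treated on this trial with pre-operative SBRT followed by surgery". The matching row of section 3.4 gives the time frame "From Day of enrollment through 36 month follow up visit".
- **Complications and wound healing.** Section 3.4 counts these from the day of surgery.
- **Analysis.** Section 12.1 promises descriptive summaries and names no denominator. Section 2 says that "statistical analysis will be descriptive and formal hypothesis-testing will not be performed".

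**The concern.** Whether an operation goes ahead and is completed is known only after radiation, and radiation may influence it. Section 9.5 lists unacceptable adverse events and changes in condition among the grounds for removal. Section 1.3.1 names bleeding and conversion to an open procedure as risks. A replacement rule tied to that outcome can select the final ten on how well they did. The only bias control offered, consecutive enrollment in section 1.4, does not protect against this, because the selection comes after enrollment.

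Section 3.2 sharpens the problem. Its wording describes survival in people who had SBRT and then surgery, while the clock in section 3.4 starts before either. Taken together, the population is conditioned on reaching an event that lies inside its own follow-up window.

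At stake is the secondary hypothesis that the regimen is well tolerated. An operable patient who is irradiated and then does not complete resection is among the most informative participants for that hypothesis, and with ten participants one such case carries weight.

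**Working it through.** The protocol gives no sample-size calculation and no expected rate of non-completion, so there is no figure of its own to reproduce. The check has three parts.

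**1. Who can be replaced, and what it touches**

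| Course after at least one fraction | Replaceable under 6.2? | Endpoints affected if dropped |
|---|---|---|
| Resection cancelled | Yes | Survival, disease outcomes, SBRT toxicity; not complications, which are counted from the day of surgery |
| Resection started, then aborted | Yes, if not regarded as successful | Those above and the complication rate |
| Death during the operation | Can be read so, as success is undefined | Those above and the complication rate |
| Death after a completed resection | No | None |

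**2. Size of the shift if one person is dropped**

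Suppose x of the 10 retained participants have an event, and one replaced participant also had it. The shift is (x + 1)/11 − x/10 = (10 − x)/110.

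- x = 0: 1/11 against 0/10, 9.1% against 0%, a shift of 9.1 points. Exact 95% intervals: 0.2% to 41.3% against 0% to about 31%.
- x = 1, for example deaths: survival 9/11 = 81.8% against 9/10 = 90%, a shift of 8.2 points.
- x = 2, for example recurrences, scoring the replaced participant as a failure: disease-free 8/11 = 72.7% against 8/10 = 80%, a shift of 7.3 points.

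With two replaced participants who both had the event, 0/10 becomes 2/12 = 16.7% (2.1% to 48.4%), and survival of 9/10 becomes 9/12 = 75%.

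If the dropped participant had no event, the shift is x/11 − x/10 = −x/110. That is −0.9 points at x = 1 and −1.8 points at x = 2: small and in the other direction. If replaced participants are kept, the shift is zero in every case.

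**3. How often the rule could come into play**

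Let q be the assumed chance that an irradiated participant does not complete surgery. The chance of at least one such case among the first 10 irradiated is 1 − (1 − q)^10. The expected number irradiated to obtain 10 completers is 10/(1 − q).

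| Assumed q | At least one in the first 10 | Expected number irradiated |
|---|---|---|
| 2% | 18.3% | 10.2 |
| 5% | 40.1% | 10.5 |
| 10% | 65.1% | 11.1 |
| 20% | 89.3% | 12.5 |

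These values of q are assumptions. They show only that the situation is not remote.

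**The case against.** The strongest reply is that replacement is not exclusion. A reader might infer that section 6.2 removes failed cases from the results and so biases them favourably. The text does not say that. Only screen failures are expressly left out of analysis (section 6.1). Follow-up continues after removal from therapy unless consent is withdrawn (9.5), all adverse events are collected (11.2), and the DSMC monitors everyone treated (14). This stands, and it makes the bias conditional. It does not settle the matter: those sections govern collection and monitoring rather than denominators, and section 3.2 does name a population.

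Three further points have force.

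- **Aborted and fatal operations are within reach of the complication endpoint.** Its window opens on the day of surgery, and death is Grade V in Appendix C. The gap is confined to whether a replaced participant is counted.
- **Monitoring is not absent before surgery.** Triggers (a) and (b) in section 12.2, the latter being "Peri operative/post-operative surgical complications beyond acceptable institutional rates as determined by study CV surgeons", presuppose an operation. A reader might infer that radiation toxicity preventing surgery would go unseen. Trigger (c) covers death from the intervention, and sections 14.1 to 14.3 provide DSMC review of serious events, their rates and overall toxicity.
- **The guaranteed-survival interval is short.** Surgery falls on days 8 to 10 of a schedule followed to month 36, although the gap from enrollment to simulation is not stated. Selection of who is counted matters more than the time itself.

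Replacement is also reasonable for the primary endpoint, which needs both a pre-SBRT biopsy and a surgical specimen. Not every non-completion would be caused by SBRT: withdrawal of consent and failed clearance fall under the same rule.

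**Conclusion.** The point holds in a conditional form. Section 6.2 ties replacement to an undefined outcome that follows treatment. Sections 3.2 and 3.4 together permit a reading in which an irradiated participant who was never resected is missing from the survival description. This is a rule fixed badly, not merely detail left to a later plan. The documents do not support the stronger claim that the results are biased as the protocol stands.

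The shift of about 7 to 9 percentage points per omitted participant assumes three things: that the person is dropped, that the person had the event in question, and that zero to two of the ten retained participants had it. No error rate is affected, because nothing is tested. Severity is moderate: the trial is a descriptive pilot and the affected endpoints are secondary.

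**What to change.** - **Section 6.2:** delete or define *successfully*. State that a participant who has received at least one SBRT fraction may be replaced only for the paired-tissue primary endpoint and stays in the toxicity and survival summaries.
- **Complication denominator:** count every operation that was started.
- **Sections 3.2 and 3.4:** describe overall and metastasis-free survival in all participants who received at least one fraction. This still conditions on starting radiation, but that is not something radiation can have influenced.
- **Results:** report the number irradiated who did not complete resection, with reasons.

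The cost is wording in three sections and one line in a results table. It adds no participants beyond those section 6.2 already permits, and no procedures, since section 9.5 already provides for continued follow-up. The downside is that reported rates may look slightly less favourable.

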7 PARTICIPANT REGISTRATION PROCEDURES

7.1 General Guidelines

Eligible participants will be registered through The University of Kansas Cancer Center Clinical Research Office central registration process and registration must occur prior to the initiation of therapy. Any participant not registered to the protocol before initiating study intervention will be considered ineligible and study intervention will be denied.

Issues that would cause study intervention delays should be discussed with the Sponsor/Investigator. If a participant does not receive protocol therapy following registration, notify The University of Kansas Cancer Center Clinical Site Management team via email at [contact] and update participant's status in the CRIS system.

7.2 Registration Process

The University of Kansas Cancer Center participant registration is accessible for registration Monday through Friday, 8:00 AM to 5:00 PM Central Time. Please allow up to 24 hours for completion of registration.

The registration procedures are as follows:

1. Obtain written informed consent prior to the performance of any study related procedures or assessments. Tests required at screening and performed as part of customary care prior to signing consent, are allowed IF those tests were performed within the timeframe listed in Participant Selection section.
2. Complete appropriate baseline demographic information in CRIS. Print, complete and obtain appropriate signatures for the inclusion/exclusion criteria to document eligibility. Maintain completed documents in participant's research record. Participants must meet all eligibility criteria to be eligible for registration.
3. Use the hyperlink at the bottom of the eligibility criteria or in the CRIS system, complete information and submit to initiate the registration process.
4. Email confirmation of registration will be sent to the person initiating the registration. Registration confirmation should be maintained as part of the participant's research record.

8 STUDY INTERVENTION PLAN

8.1 Radiation Treatment Regimen

Study Intervention	Dose	Schedule	Cycle Length
SBRT	800 cGy x 3 fractions	Daily	5-7 days prior to planned surgery

RADIATION THERAPY

Modalities:

Stereotactic Body Radiation Therapy has now been formally defined and described in a published guideline from the American College of Radiology and American Society for Therapeutic Radiology and Oncology.^{19,20}

This protocol will follow that guideline.

Dose Fractionation

Patients will receive 2400 cGy in 3 fractions of 800 cGy/fraction to the prescription line at the edge of the PTV (see section below with title *Prescription Dose Constraints for Treatment Planning* for more prescription details). Treatment delivery will be scheduled for 3 consecutive days, but may be modified as needed by the treating radiation oncologist.

A minimum of 18 hours between fractions is required.

Technical Factors

- **Physical Factors**

Only photon (x-ray) beams produced by linear accelerators, with photon energies of 6-15 MV will be allowed.

- **Dose Verification at Treatment**

Patient specific QA will be performed for each patient prior to first fraction. Additionally, in-vivo dosimeter measurements (e.g., TLD/NanoDots/Mosfet) may be obtained for surface dose verification for accessible beams as per institutional preference.

Localization, Simulation, and Immobilization

- **Patient Positioning**

Patients will be positioned in a reproducible position. A variety of immobilization systems may be used.

- **Inhibition of Effects of Internal Organ Motion**

Special considerations must be made to account for the effect of internal organ motion (e.g., breathing) on target positioning and reproducibility. Acceptable maneuvers include reliable abdominal compression, accelerator beam gating with the respiratory cycle, tumor tracking, and active breath-holding techniques.

Localization.

- IGRT will be required with CBCT images obtained prior to each fraction and verified by treating physician prior to treatment delivery.

Treatment Planning/Target Volumes

- Computed tomography will be the primary image platform for targeting and treatment planning. The target lesion will be outlined by the treating physician and will be designated as the gross tumor volume (GTV), which will also be designated the clinical target volume (CTV)(i.e. GTV=CTV). 4DCT data sets will be used to generate internal tumor volume (ITV). The PTV will include the ITV plus an additional 0.5 cm margin uniformly applied to the ITV. Per physician discretion, these volumes can be adjusted based on each patient's clinical situation and anatomy.

Dosimetry

- Three-dimensional coplanar or non-coplanar beam arrangements will be custom designed for each case to deliver highly conformal prescription dose distributions. Non-opposing, noncoplanar beams are preferable. For purposes of dose planning and calculation of monitor units for actual treatment, this protocol will require tissue density heterogeneity corrections.

Prescription Dose Constraints for Treatment Planning

The prescription isodose surface will be chosen such that 95% of the target volume (PTV) is conformally covered by the prescription isodose. Dose homogeneity within the GTV of +/- 5% is highly recommended.

Organs At Risk (OAR) visible in the planning CT will be contoured. Dose constraints are defined below.

Dose Constraints

- Modification as defined in the chart below** of the Dose Constraints as defined by RTOG 9501 Arm 2 12 Gy X 4 is the basis of dose limitations of the organs at risk to be used this protocol.²¹
- The risk of end-organ damage as defined in the table is anticipated to be less than 1%.**

Organ at Risk	Volume	Volume Max (Gy)	Max Point Dose (Gy)	Endpoint (\geq Grade 3)
Spinal Cord	<0.35 cc <1.2 cc	10.4 Gy (5.2 Gy/fx) 6.8 Gy (3.4 Gy/fx)	13 Gy (6.5 Gy/fx)	Myelitis
Esophagus	<5 cc	9.4 Gy (4.7 Gy/fx)	15 Gy (7.5/fx)	Stenosis/fistula
Brachial Plexus	<3 cc	11.8 Gy (5.9 Gy/fx)	13.6 Gy(6.8Gy/fx)	Neuropathy
Heart/Pericardium	<15 cc	14 Gy (7 Gy/fx)	17 Gy (8.5 Gy/fx)	Pericarditis
Great vessels	<10 cc	21.5 Gy (10.75 Gy/fx)	24.5 Gy (12.25 Gy/fx)	Aneurysm
Trachea and Large Bronchus	<4 cc	7.8 Gy (3.9 Gy/fx)	17.4 Gy (8.7 Gy/fx)	Stenosis/fistula
Rib	<1 cc	16 Gy (8 Gy/fx)	20 Gy (10Gy/fx)	Pain or fracture
Skin	<10 cc	16.6 Gy (8.3 Gy/fx)	18 Gy (9 Gy)	Ulceration
Stomach	<10 cc	8.8 Gy (4.4 Gy/fx)	18.6 Gy (6.8 Gy)	Ulceration/fistula
Parallel Tissue	Critical Volume (cc)	Critical Volume Dose Max (Gy)		Endpoint (\geq Grade 3)
Lung (Right & Left)	1500 cc	5.8 Gy (2.9 Gy/fx)		Basic Lung Function
Lung (Right & Left)	1000 cc	6.2 Gy (3.1 Gy/fx)		Pneumonitis

Quality assurance

Patient safety will be ensured with effective treatment delivery with a robust quality assurance protocol as defined below.

- Prior to treatment each patient will be discussed by quality assurance team as defined by a study investigator, treating radiation oncologist, study physicist and dosimetrist.
- The treating radiation oncologist will confirm prior to the first fraction delivery that the radiation treatment plans must meet target dose levels for dose homogeneity..
- Prior to plan approval, the organ at risk dose volume histogram must be verified by the treating radiation oncologist and physicist. Dose constraints as defined shall not be exceeded.

- Image-guided radiation treatment (I GRT/SBRT) with cone beam CT will be used to verify patient positioning prior to each treatment. And will require approval by the treating radiation oncologist prior to treatment delivery.

Possible side effects of SBRT as listed below.

The likelihood of the defined organ risk/toxicity is anticipated to be less than 1%, as the dose constraints defined in this protocol are well below the RTOG-0915 defined dose constraints for SBRT of the lung.

Organ at Risk	Possible Side Effect	Volume	Volume Max (Gy) Dose threshold as defined for end organ damage in RTOG 0915
Spinal Cord	Myelitis	< 0.35 cc < 1.2 cc	20.8 Gy (5.2 Gy/fx) 13.6 Gy (3.4 Gy/fx)
Esophagus	Stenosis/fistula	< 5 cc	18.8 Gy (4.7 Gy/fx)
Brachial Plexus	Neuropathy	< 3 cc	23.6 Gy (5.9 Gy/fx)
Heart/Pericardium	Pericarditis	< 15 cc	28 Gy (7 Gy/fx)
Great vessels	Aneurysm	< 10 cc	43 Gy (10.75 Gy/fx)
Trachea and Large Bronchus	Stenosis/fistula	< 4 cc	15.6 Gy (3.9 Gy/fx)
Rib	Pain or fracture	< 1 cc	32 Gy (8 Gy/fx)
Skin	Ulceration	< 10 cc	33.2 Gy (8.3 Gy/fx)
Stomach	Ulceration/fistula	< 10 cc	17.6 Gy (4.4 Gy/fx)
Parallel Tissue	Possible Side Effect	Critical Volume (cc)	Critical Volume Dose Max (Gy)
Lung (Right & Left)	Basic Lung Function	1500 cc	11.6 Gy (2.9 Gy/fx)
Lung (Right & Left)	Pneumonitis	1000 cc	12.4 Gy (3.1 Gy/fx)

Surgery

- Surgery will occur 5 to 7 days post completion of the last fractionation of radiation treatment. Surgery will consist of a lobectomy or sub lobar resection. The technique will be at the discretion of the study cardiothoracic surgeon, and may employ either an open approach, video assisted thoracoscopic or robotic-assisted approach. Surgical sampling of the at risk hilar and mediastinal nodes may be performed at the time of resection but is not a requirement of the study.
- In the event adjuvant systemic therapy is elected, follow up studies as defined in this protocol may be modified as clinical necessity requires. Participants will be continued for secondary objectives and will be reported using descriptive statistical analysis.

Pathology Processing

- After resection, the tumor will be oriented by the surgeon and submitted to the pathology lab. In the pathology lab it will undergo gross examination in a standard manner. The specimen will be submitted for microscopic examination. Samples for translational research use will be processed and transferred to the appropriate laboratory as defined in the study laboratory manual.

